9.1.3. Safety Analysis Set

A group of subjects who receive at least one dose of investigational drug is defined as the "safety analysis set". The safety analysis set will be used for the analysis of safety endpoints.

9.1.4. PK Analysis Set

The "PK analysis set" will consist of all subjects who receive at least one dose of investigational drug and have at least one point of drug plasma or urine concentration data. PK analysis set will be used for the analysis of PK endpoints.

9.2. Sample Size Considerations

The required sample size of 55 is calculated in SAS[®] POWER Procedure using Fisher's exact test, when the one-sided significance level is 5% with a statistical power of 90%, with the expected overall response rate (ORR) of 25% and the 10% threshold. Considering for the subjects who are excluded from analysis resulting from the central pathological diagnosis, the planned sample size is 65 subjects.

9.3. Interim Analysis

No interim analysis and no early termination for efficacy are planned in this study.

An interim review for efficacy and safety including PK as needed [See Section 8.5.2] will be performed at the point when the number of efficacy evaluable subjects evaluable for efficacy reaches 20 and have all necessary data available.

9.4. Planned Methods of Analysis

Upon submission of the New Drug Application for SP-02L, an appropriate data cut-off date should be determined as the primary endpoint is evaluable. Detailed analytical method in this study will be specified in the statistical analysis plan.

In this study, no analysis will be performed considering withdrawal. No imputation for missing values will be performed. No adjustment for covariates, the investigational sites or multiplicity will be performed.

9.4.1. Data summarization

Of the demographic variables and baseline (subject background factors) and data, continuous variables will be summarized by n, mean, standard deviation (or standard error for efficacy), median, Q1, Q3, minimum, and maximum values. Categorical variables will be summarized by frequency and percentage.

9.4.2. Analysis of Efficacy Endpoints (Tumor Response)

Based on a central assessment of tumor response at Efficacy and Safety Review Committee, the best overall responses for 6 cycles will be summarized to calculate the ORR and 90% confidence interval (90% CI). Based on a local assessment at each investigational site, the best overall responses for 6 cycles and in the entire period will be summarized to calculate ORR and 90% CI.

The best overall response will be summarized and the ORR will be calculated by histopathological classification, clinical stage according to Ann Arbor classification, prognosis risk group according to international prognostic index (IPI), prognosis risk group based on Prognosis Index for T-cell lymphoma (PIT), ethnic background, sex and age (< 61 years old or ≥ 61 years old).

To assess the tumor response in each subject, the waterfall plot will be produced to show the rate of tumor shrinkage at best overall response.

9.4.3. Analysis of Efficacy Endpoints (Survival Time and Others)

Progression-free survival (PFS), time to response (TTR), duration of response (DOR) and overall survival (OS) will be summarized overall and by histopathological subtype. PFS and OS will be analyzed by using Kaplan-Meier method overall and by histopathological subtype.

Progressive disease (PD), relapsed disease (RD) or death which occurs earlier is defined as “progression event”, and “the date of progression” will be identified for analyses of PFS and DOR in accordance with the following rules:

- The date of judgment of PD or RD based on the radiological assessment of tumor response [See Section 6.14.2] is defined as “the date of progression”.
- PD or RD includes not only the results of radiological assessment with imaging data but “symptomatic progression” at the principal investigator’s or sub-investigator’s judgement based on clinical symptoms or laboratory findings, etc. In this case, the date of the investigator’s judgement is defined as “the date of progression”.

- If “death” occurs earlier than the judgement of “PD” or “RD”, the date of death is defined as “the date of progression”.

If no progression event is confirmed prior to the following events, the most recent date (date of the last day) of radiological assessment of tumor response [See Section 6.14.2 will be defined as “the date of censoring”]:

- Subsequent anticancer treatment for primary disease initiated
- Investigational drug is discontinued for toxicity (investigational-drug-related AEs)
- Subject is lost to follow up

If a subject is surviving on the date of “data cut-off”, the most recent date (date of the last day) of confirmation of subject’s existence is defined as “the date of censoring” for the analysis of OS. For a subject lost to follow-up, the last date when the subject’s existence is confirmed prior to the subject’s lost to follow-up is defined as “the date of censoring”.

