2.5.2. Secondary Endpoints

Secondary endpoints of this study are as follows. "Response" is defined as "complete response (CR)" or "partial response (PR)".

- Progression-Free Survival (PFS)
Defined as the time from the first day of investigational drug administration (Day 1 of Cycle 1) to the date of "progressive disease (PD)" or "relapsed disease (RD)", or the date of "death", which occurs earlier
- Time To Response (TTR)
Defined as the time from the first day of investigational drug administration (Day 1 of Cycle 1) to the first day of tumor response observed for patients who achieved a CR or PR
- Duration of Response (DOR)
Defined as the time from the first day of tumor response observed for patients who achieved a CR or PR to the date of PD or RD, or the date of "death", which occurs earlier
- Overall Survival (OS)
Defined as the time from the first day of investigational drug administration (Day 1 of Cycle 1) to the date of "death" from any cause
- Occurrence of adverse events (AEs)
- Drug plasma concentration-time profile, PK parameters, and urinary excretion rates

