6.15. Survival Surveillance

6.15.1. Surveillance of Progression of Disease and Relapsed Disease

If PD, RD or “death” is not confirmed by the end of follow-up period, tumor response assessment [See Section 6.14.2] will be continued at intervals of three months or less until PD, RD or “death” is confirmed.

PD or RD includes not only the results of the radiological assessment with imaging data but also “symptomatic progression” at the principal investigator’s or sub-investigator’s judgement based on clinical symptoms or laboratory findings, etc. The development of secondary cancer is not defined as progression event, and surveillance of PD, RD or “death” will be continued.

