11.6 Analyses for Survival Time

PFS, TTR, DOR and OS will be summarized to calculate lower quartile, median, upper quartile and their 90%

CI by using Kaplan-Meier method in total and by ethnic background (Japanese, Except Japanese, Korean, Taiwanese, Hong Konger/Chinese and others). As for PFS and OS, Kaplan-Meier curve will be displayed. The same analysis will be performed by histopathological subtypes (PTCL-NOS, AITL, ALCL ALK-positive, ALCL ALK-negative, other lymphoma).

"Progressive disease (PD)", "Relapsed disease (RD)" or "death" which occurs earlier is defined as "progression event", and "the date of progression" will be identified for analyses of PFS and DOR in accordance with the following rules:

- The date of judgment of PD or RD based on the local assessment of tumor response by investigator at each site (cf. Section 6.14.2 of protocol) is defined as "the date of progression".
- PD or RD includes not only the results of tumor response assessment based on diagnostic imaging data but also investigator's clinical judgment of "Symptomatic Progression" based on clinical symptoms and findings, and clinical laboratory test result, etc.). In this case, the date of the judgement is defined as "the date of progression".
- If "death" occurs earlier than the judgement of "PD" or "RD", the date of death is defined as "the date of progression".

If no progression event is confirmed prior to the following events, the most recent date of local assessment of tumor response will be defined as "the date of censoring":

- Subsequent therapy for primary disease is initiated
- Investigational drug is withdrawn due to adverse drug reaction
- Subject is lost to follow up

If a subject is surviving on the date of data cut-off, the most recent date of confirmation of subject's existence is defined as "the date of censoring" for the analysis of OS. For a subject lost to follow-up, the last date when the subject's existence is confirmed prior to the subject's lost to follow-up is defined as "the date of censoring". If treatment-duration exceeds 2 years, the date after 2 years is defined as "the date of censoring".

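### PFS and DOR are censored when the drug is stopped for toxicity, so progressions and deaths that the protocol goes on to collect are left out, contrary to its own endpoint definitions

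*Protocol*

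**What the plan says.** **Definitions.** For PFS, Protocol 2.5.2 starts the clock at first dose ("Defined as the time from the first day of investigational drug administration (Day 1 of Cycle 1) to the date of" opens the definition) and stops it at progression, relapse or death. DOR runs from first response "to the date of PD or RD, or the date of 'death', which occurs earlier". The protocol glossary and the SAP list of terms agree. None of them limits either endpoint to time on treatment.

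**Analysis rule.** Protocol 9.4.3 sets the censoring date for subjects without an earlier event ("If no progression event is confirmed prior to the following events, the most recent date (date of the last day) of radiological assessment of tumor"): the day of the last such assessment is used. Three triggers follow: subsequent anticancer treatment, toxicity ("Investigational drug is discontinued for toxicity (investigational-drug-related AEs") and loss to follow-up. SAP 11.6 has the same list, with "Investigational drug is withdrawn due to adverse drug reaction" as its toxicity trigger and the last local assessment as the censoring date.

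**Follow-up.** Under Protocol 6.15.1, for a subject with no event by the end of the follow-up period, tumor assessment "will be continued at intervals of three months or less until PD, RD or" death. There is no exception for subjects who stopped for toxicity. Protocol 6.15.3 follows survival for up to 2 years from first dose.

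Neither document gives a reason for the toxicity trigger, restates the endpoints as on-treatment measures, or plans a PFS or DOR analysis that counts the later events.

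**The concern.** The analysis rule and the endpoint definitions disagree. A subject who stops for a drug-related event and later progresses or dies has had the event that PFS and DOR are defined to capture, and the protocol arranges to observe it. The analysis then treats that subject as event-free at the last assessment.

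Kaplan-Meier is valid only if censored subjects have the same future risk as those still followed. Subjects who stop for toxicity lose the study drug and may be frailer, so that cannot be taken for granted. In a single-arm trial, PFS and DOR are the reported evidence of durability, with no control arm in which a similar bias might partly cancel.

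**Working it through.** **1. The plan's own figure.** The only design calculation is for ORR (Protocol 9.2: 10% versus 25%, one-sided 5%, power 90%, n = 55). An exact one-sample binomial calculation agrees. With at least 10 responses required, n = 54 gives alpha 0.0398 and power 0.899, and n = 55 gives alpha 0.0444 and power 0.911. This point does not affect that figure. No corresponding figure exists for PFS or DOR.

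**2. Two subjects traced through the text.**
- *Progression after a stop.* The drug is stopped for a related event, no new therapy starts, and progression is found at a later assessment under 6.15.1. By 2.5.2 this is an event. By 9.4.3 no event preceded the stop, so the subject is censored.
- *A responder.* Response is first documented at the Cycle 3 scan and the drug is stopped for toxicity before the Cycle 6 scan. If the last scan before the stop is used, DOR is censored on the day it began and contributes no follow-up time.

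**3. Illustrative size for PFS.** All rates here are assumptions.
- PFS is exponential with median m = 2, 3 or 6 months, so the hazard is λ = ln 2 / m.
- A share q = 5%, 10% or 20% stops for toxicity before progression, so the stopping hazard is μ = λq/(1 − q).
- After a stop the hazard is kλ, with k = 1, 2 or 3. Follow-up is capped at 24 months.
- Scans are every 3 cycles: 63 days, or 63/30.4375 = 2.07 months.
- Each scenario has 400,000 simulated subjects. No competing subsequent-therapy censoring is included.

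The rule was applied with two censoring dates: the last scan before the stop (day 0 if the stop precedes the first scan), and the stop date itself. The second approximates use of a scan close to the stop. Selected results, medians in months:

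| m | q | k | Events dropped, of 55 (of 65) | Median, all events counted | Censored at prior scan | Censored at stop |
|---|---|---|---|---|---|---|
| 3 | 5% | 1 | 2.7 (3.2) | 3.00 | 2.96 (-1.3%) | 3.00 (0%) |
| 3 | 5% | 3 | 2.7 (3.2) | 2.93 | 2.96 (+1.0%) | 3.00 (+2.4%) |
| 2 | 20% | 1 | 11.0 (13.0) | 2.00 | 1.85 (-7.5%) | 2.00 (0%) |
| 3 | 20% | 1 | 10.8 (12.8) | 2.99 | 2.82 (-5.7%) | 2.99 (0%) |
| 3 | 20% | 3 | 11.1 (13.1) | 2.72 | 2.84 (+4.4%) | 3.01 (+10.7%) |
| 6 | 20% | 3 | 10.4 (12.3) | 5.41 | 5.81 (+7.4%) | 5.98 (+10.5%) |

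Over all scenarios the rule drops 2.1 to 11.1 events of 55 (2.5 to 13.1 of 65). With different assumptions (medians of 3 or 6 months, 5% to 17% of subjects prone to stop at 0.5 to 4 months, hazard 1 to 3 times baseline), the shift in the median ran from -4.9% to +10.4%.

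Two effects oppose each other. Cutting time back to an earlier scan lowers the median. Removing subjects at raised risk increases it.

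**4. DOR.** Expected responders: 0.25 × 55 = 13.75, about 14. One toxicity stop among them affects 1/14 = 7%, and two affect 2/14 = 14%.

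**The case against.** **The subsequent-therapy trigger departs from the definition in the same way.** That is true, so the disagreement is not unique to toxicity. The cases still differ. After new therapy starts, time to progression also reflects that therapy. After a toxicity stop without new therapy, it still reflects only the course of study drug.

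**Toxic deaths mostly count.** A death before any decision to stop is an event under 9.4.3. This is correct. Only deaths after a stop are lost.

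**The censoring date is ambiguous.** Neither document says that the last assessment must precede the stop; it could be the end-of-treatment scan at Day 15 to 42 of the last cycle (Protocol 6.14.2). This stands. Under that reading the downward shift largely disappears and the upward one remains.

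**The size is speculative and modest.** This also stands. The phase 1 figure of 4 of 23 (17%) is a rate of related Grade 3 or higher events, not of discontinuation, and it is not a firm upper bound because Protocol 5.4.3 allows stops for lesser events. Nothing in the documents supports a tripled hazard. Subsequent therapy would censor some of these subjects anyway, so the counts above are at the upper end. For an uncensored exponential sample, the 90% interval for the median has relative half-width 1.645/(√n × ln 2): 32% at n = 55 and 29% at n = 65. The shift lies well inside it. Sampling error does not excuse a systematic departure from the definition, however, and the data to avoid it are collected.

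**A sensitivity analysis would be enough.** That would leave the main estimate describing something other than the stated endpoint.

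**Conclusion.** The concern holds. As written, the plan censors subjects who stop for drug-related toxicity, continues to collect their progressions and deaths, and leaves those events out of endpoints whose definitions include them. This follows from the text and needs no assumption.

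The size does rest on assumptions. With 5% to 20% of subjects stopping for toxicity, about 2 to 11 of 55 PFS events would be lost and the reported median would move by roughly -8% to +11%. The direction depends on prognosis after stopping and on which assessment supplies the censoring date. DOR is more fragile, since one or two stops affect 7% to 14% of about 14 responders.

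ORR and its sample size, TTR and OS are untouched, and no hypothesis test of PFS or DOR is planned. The change should be made, but it does not bear on the primary conclusion.

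**What to change.** Delete the toxicity trigger from Protocol 9.4.3 and SAP 11.6. State that progression or relapse (including symptomatic progression) or death counts whenever it is observed, and that event-free subjects are censored at their last adequate assessment before data cut-off or loss to follow-up. This also fills a gap: the present PFS and DOR triggers do not cover subjects who are event-free at cut-off. The subsequent-therapy trigger can stay. The current toxicity rule may be kept as a labelled sensitivity analysis, with its censoring date made explicit.

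The cost is a wording change in two documents and at most one extra table. Protocol 6.15.1 already provides the follow-up, so no visits, scans or changes to patient management are needed.

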9.4.4. Analysis of Safety Endpoints

The incidence of AEs will be summarized by system organ class and by preferred term according to the ICH-MedDRA, and by ethnic background and severity. Incidence of investigational-drug-related AEs, serious AEs (SAEs) and investigational-drug-related SAEs will be also summarized, respectively, in the same way.

SAEs, SAEs of \geq Grade 3, and significant AEs in the judgement of the Development Sponsor; e.g. neurological disorder and psychiatric disorder, will be summarized or described.

Vital signs, laboratory values and ECG parameters will be summarized by item and time point.

9.4.5. PK Analysis

Plasma drug concentrations will be summarized overall and by ethnic background, and the graphs of mean plasma drug concentration-time profiles will be provided. The following PK parameters for each subject will be estimated using non-compartmental methods and summarized overall and by ethnic background.

- Maximum drug concentration time: t_{max}
- Maximum drug concentration: C_{max}
- Area under the blood concentration time curve: AUC_{0-t} and $AUC_{0-\infty}$
- Half-life period: $t_{1/2}$
- Systemic clearance: CL
- Distribution volume: Vd_{ss} and Vd_z
- Mean retention time: MRT_{last}

Urine excretion rates will be calculated and summarized overall and by ethnic background.

9.4.6. Additional Analyses

At the discretion of the Development Sponsor, additional analyses of the data will be conducted as deemed appropriate. Details of additional analyses are specified in the statistical analysis plan.

10. STUDY ADMINISTRATION AND ETHICAL CONSIDERATIONS

10.1. General Ethical Requirements

This study will be conducted in accordance with the ethical principles of the Declaration of Helsinki, ICH-GCP, country- and region-specific GCP, the currently approved protocol/amendment(s) of this study, the clinical trial contract that is concluded between each investigational site and the Sponsor (and CRO), and other agreements that are concluded between the medical institution and the Sponsor (and CRO).

10.2. Protocol Management

The Sponsor provides the protocol and an example of informed consent form, and sample of eCRF as needed to the principal investigator. Any amendment of these documents will be promptly notified to the principal investigator with the reason for amendment, except when necessary to eliminate immediate hazards to the subjects [See Section 8.4] or when the change(s) involves only logistical or administrative aspects of the trial (e.g., change of the name or address of investigational site, name and title of principal investigator, name and address of the Sponsor or CRO, and name, title and contact information of monitors)

The Sponsor should obtain the principal investigator's agreement for the protocol or amendments if the protocol is amended and to conduct the study in compliance with the protocol. To confirm this agreement, the Sponsor and investigator will sign and date on the page of "Investigator's Agreement" in the protocol or any alternative document. The Sponsor will designate a Study Manager in each of participating country or region as a person who is authorized to represent the Sponsor and sign the above document.

10.3. Quality Control and Quality Assurance

The Sponsor and CRO are responsible for implementing and maintaining quality assurance and quality control systems with written SOPs.

10.3.1. Monitoring and Audit

Monitors will visit the investigational sites and carry out the monitoring. The purposes of study monitoring are to verify that the rights, safety and well-being of human subjects are protected, the conduct of the trial is in compliance with the currently approved protocol/amendment(s), with GCP, and with the applicable regulatory requirement(s), and the data entered in eCRF and in other study reports are accurate, complete and verifiable from source documents.

The auditors should evaluate study conduct and compliance with GCP and the protocol, as quality control functions, according to the audit plan. The observations and findings of the auditor(s) should be documented and submitted to the Sponsor. A global auditor who is appointed by the Development Sponsor may visit the CROs and the investigational sites in each country or region to evaluate study conduct in each country or region to confirm the compliance of the study with the ICH-GCP from a unified perspective (Global Audit).

10.3.2. Direct Access to Source Documents

The principal investigator and medical institutions are required to permit direct access to all study-related documents, data, and records, including source documents related to the subject's original medical records and data, on the occasion of monitoring and auditing by the Sponsor or CRO as well as the inspection by the IRB or domestic and foreign regulatory authorities. The principal investigator or sub-investigator is obligated to inform and obtain the written consent of each subject to permit the direct access to the subject's source documents related to the subject's original medical records and data, on the occasion of monitoring and audit as well as the site inspection by the IRB or regulatory authorities.

10.4. Retention of Study Records

The principal investigator and the investigational site, including IRB and person in charge of the management of the investigational drug, should not destroy, without prior agreement with the Sponsor or CRO, any study-related documents or records, in conformance with ICH-GCP and country- or region-specific GCP.

The Sponsor or CRO should notify the principal investigator or the investigational site in writing when these documents no longer need to be retained (at the end of retention period).

10.5. Subject Confidentiality

The principal investigator and the investigational site must ensure that subject's confidentiality is maintained as follows:

- On data, documents and records submitted to the Sponsor or CRO, such as data entered into eCRFs and the Serious Adverse Events Reports, a subject should be identified by a subject number only.
- Data and documents that are not for submission to the Sponsor or CRO, including signed informed consent forms, should be kept in strict confidence at the investigational site.

Employees of the Sponsor and the CRO, whether incumbent or not, should not disclose, without legitimate reasons, any confidential information obtained through direct access to the source documents.

